8.0 Patient Assessments

8.1

Study Parameters

Assessment	Pre TX	1 Mo Post TX	6 MO Post TX then every 6 months	6 MO Post TX then annually
H & P	X	X	X*	
Disease Status	X	X	X*	
Toxicity Assessment	X	X	X*	
Mammo	X			X
CBC & LFT	X	As indicated	As indicated	As indicated
Bone scan or CT scan	As needed	As indicated	As indicated	As indicated
Photos	X			X
Cosmesis Assess. (MD&Pt.)			X	X
Chest X-ray	X			X

* Until year 5 at which time complete assessment will be conducted annually

8.2

Definitions for Cosmetic Outcomes

Cosmetic outcome will be graded by the study subject, radiation oncologist, and surgical oncologist periodically following treatment according to section 8.1. The grading scale will be as follows:

Excellent – the treated breast, when compared to the untreated breast, shows minimal or no changes in shape or size. There may be minimal subcutaneous fibrosis or scarring.

Good – there are mild changes in the size and shape of the treated breast. Scarring within the breast causes mild alterations

in breast shape.

Fair – there is a clear difference in the size and/or shape of the treated breast that involves $\frac{1}{4}$ or less of the treated breast.

Poor – marked changes in the treated breast that involves more than $\frac{1}{4}$ of the breast.

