8.3 Photographs

Photographs will be taken of the post-surgical breast and periodically following proton therapy per section 8.1. These will be used to document cosmetic outcome. Photos will include a “close up” view of the treated breast with the subjects arms raised over the head and a photo of both breasts with the subjects hands on hips. Photographs will not include the subjects’ face.

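### Cheap improvement: no cosmesis grade is planned before proton therapy, so the grades describe lumpectomy plus protons and cannot show which breasts were already fair or poor after surgery

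*Combined protocol and SAP*

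**What the plan says.** Cosmesis is one of the trial's stated aims (Objective 2.3). On who grades and when, section 8.2 states: "Cosmetic outcome will be graded by the study subject, radiation oncologist, and surgical oncologist periodically following treatment according to section 8.1".

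In the section 8.1 table, the cosmesis row (physician and patient) has no mark in the pre-treatment column or the 1-month column. Its marks stand under "6 MO Post TX then every 6 months" and "6 MO Post TX then annually". By contrast, history and physical, "Toxicity Assessment" and photographs are all marked before treatment.

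The four-grade scale in 8.2 takes the other breast as its reference. The top grade applies when "the treated breast, when compared to the untreated breast, shows minimal or no changes in shape or size", and the definitions of the two upper grades also mention scarring.

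Section 8.3 plans photographs of the breast after surgery and again after protons. It says of them: "These will be used to document cosmetic outcome". One of the views is "a photo of both breasts with the subjects hands on hips". No section names a grader or a scale for the photographs, or a comparison of the pictures before and after protons. Section 9 plans tabulations of toxicity (9.2) and recurrence (9.3) but none of cosmesis.

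**The concern.** Lumpectomy, and re-excision where it is done (3.6), can change the size and shape of the breast and leave scars before the first proton treatment. A scale anchored to the untreated breast counts all of that. Someone who reads a grade of fair at 6 months cannot tell from the planned grades whether the breast was already fair when radiotherapy began or became so afterwards.

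The Introduction expects that better dose homogeneity with protons may improve cosmetic results, so readers will want to know how much of an unfavourable grade was there beforehand. If the plan is followed as written, an in-person grade before protons is never collected, and it cannot be collected in person once treatment has begun.

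**Working it through.** The documents give no target rate, sample-size argument or analysis for cosmesis, so there is no figure to reproduce. The check has two parts.

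**1. Is a pre-proton grade planned anywhere?**

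| Source | Before protons | 1 month | From 6 months |
|---|---|---|---|
| 8.1, cosmesis row | blank | blank | marked |
| 8.2, text | not mentioned | not mentioned | graded after treatment, as set out in 8.1 |
| 8.1 and 8.3, photographs | marked; breast after surgery | blank | marked in the annual column |
| Section 9 | no cosmesis analysis | – | – |

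The table and the text agree, so the blank cell is unlikely to be an accident of how the table was read. What is missing is the grade. The picture of the breast before protons is planned.

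**2. How much can the missing grade hide?**

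Let *n* be the number graded at follow-up, *x* the number fair or poor at follow-up, and *b* the number already fair or poor after surgery. If all *b* stay fair or poor, the rate of new fair or poor results among breasts that were good or excellent before protons is

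(*x* − *b*) / (*n* − *b*).

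The values of *x* and *b* below are assumptions, because the documents give none. Two sizes are shown: 50, which is the Schema figure, and 100, which is the sum of the 50 and the additional 50 in section 9.1.

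| *n* | *x* (observed) | *b* (not recorded) | New fair/poor |
|---|---|---|---|
| 100 | 20 | 0 | 20/100 = 20.0% |
| 100 | 20 | 5 | 15/95 = 15.8% |
| 100 | 20 | 10 | 10/90 = 11.1% |
| 100 | 20 | 20 | 0/80 = 0% |
| 50 | 10 | 0 | 10/50 = 20.0% |
| 50 | 10 | 3 | 7/47 = 14.9% |
| 50 | 10 | 5 | 5/45 = 11.1% |
| 50 | 10 | 10 | 0/40 = 0% |

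Within each size, every row gives the same observed result, 20% fair or poor. The planned grades cannot tell the rows apart. A larger sample would not help, because *b* is not estimated at all.

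The range of 0% to 20% depends on the persistence assumption. If breasts that were fair or poor after surgery can improve, the range is wider: with *n* = 100, *x* = 20 and *b* = 20, and all 20 improving, the 20 seen at follow-up would all be new, which is 20/80 = 25%.

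**The case against.** The strongest reply is that the combined result is the natural target. The trial's title joins lumpectomy and proton therapy, the scale is anchored to the untreated breast, and section 9 claims no change from baseline. The only cosmesis benchmark in the protocol, good or excellent in more than 75% of patients in earlier partial-breast studies (section 1.0), is a percentage of treated patients and can be set beside the planned grades. All of this stands. A reader might infer that Objective 2.3 cannot be met; the documents do not support that.

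The second reply is that baseline material exists. This is largely right. A reader might infer that the trial holds no cosmetic baseline, or that the patient's own view before protons is lost beyond recovery. Neither follows: physicians and patients could both grade a stored pre-treatment photograph later, and the view of both breasts suits the scale. But that would be a retrospective grade of an image. It is not a rating made at the time, and it cannot show palpable fibrosis, which the definition of the top grade mentions.

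It is also tempting to say that photographs miss about half of the grading visits. The documents do not settle this. Cosmesis is marked in both the 6-monthly and the annual column. If grading is in fact annual, photographs fall at every grading visit. Nor can a firm upper limit be put on the time from surgery to the first grade: no visit windows are given, and 5.4.1 does not say that the ten treatment days are consecutive.

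Finally, the gain is limited. With no control arm, a shift from the pre-proton grade also contains surgical healing and any systemic therapy given after protons (7.1). A table of worsened grades could be over-read as a proton effect, so it must carry a descriptive label.

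**Conclusion.** The point holds as an inexpensive improvement to how Objective 2.3 can be interpreted. It is not a failure of the objective, a safety matter or a sample-size problem. No cosmesis grade is planned before protons, and the scale takes in the effect of surgery. The planned grades therefore cannot separate new from pre-existing fair or poor results. In the illustration, one observed rate of 20% fits a new rate anywhere from 0% to 20%; this rests on assumed counts and on the assumption that post-surgical fair or poor grades persist. The statement that no grade is planned rests on the text of 8.1 and 8.2 alone and needs no assumption.

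**What to change.** 1. In 8.1, mark the pre-treatment column of the cosmesis row for physicians and patient.
2. In 8.2, add that grading also takes place before proton therapy, after surgery is complete, with the same four grades and the same three raters.
3. In section 9, add one line: separately for each rater, tabulate follow-up grade by pre-proton grade, beside the percentage good or excellent with its exact 95% confidence interval, all labelled descriptive. State there that the shift includes surgical healing and later systemic therapy and is not an estimate of a proton effect.
4. For patients already treated, grade the stored pre-treatment photographs on the 8.2 scale, and report these grades apart from the in-person grades.

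The cost is one short rating per rater before protons, so up to three per patient, plus the time to grade stored photographs. No new procedure or staff is needed. The documents do not say whether the examination and photographs share one visit or whether the surgical oncologist attends, so that rating may need to be arranged. Earlier patients will have only photograph-based baselines. Accrual to date is not stated; if the change began with the 50 subjects added in 2008 (an assumption), at most 50 of 100 would have an in-person baseline from all three raters.

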8.3 Photographs

Photographs will be taken of the post-surgical breast and periodically following proton therapy per section 8.1. These will be used to document cosmetic outcome. Photos will include a “close up” view of the treated breast with the subjects arms raised over the head and a photo of both breasts with the subjects hands on hips. Photographs will not include the subjects’ face.

9.0 Statistics and Data Management

9.1 Initially 25 subjects will be enrolled into this trial. After a toxicity evaluation is completed and felt to be acceptable, 25 additional subjects will be enrolled for a total of 50 subjects.

An additional 50 subjects will be enrolled under the new eligibility criteria defined in the April 4, 2008 revision.

9.2 All acute toxicities will be scored according to the NCI Common Toxicity Criteria v2.0. Late toxicity will be scored per RTOG guidelines. Any toxicities with a threshold of Grade 3 or above will be reported as an adverse event. Frequencies of toxicities will be tabulated and compared to published reports.

9.3 Frequency and type of recurrence (local, regional, distant) will be tabulated and compared to prior studies.

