2.0 Objectives

- 2.1 To evaluate the technical feasibility of delivering partial breast irradiation with proton beam.
- 2.2 To evaluate the acute and long term toxicity associated with partial breast proton therapy.
- 2.3 To evaluate the cosmetic results with partial breast proton therapy
- 2.4 To determine the local tumor control and survival associated with partial breast proton therapy.

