5.4 Dose, Fractionation and Treatment

- 5.4.1 40 CGE will be delivered to the CTV in 10 equal fractions over ten treatments days.
- 5.4.2 At least 2 fields will be treated each day.
- 5.4.3 Orthogonal localization radiographs to be taken prior to each treatment with surgical clips used as localizing markers.

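### Acute toxicity is to be scored in full, but schedule 8.1 has no toxicity score during or at the end of treatment and no worst-grade or recall rule for the 1-month visit

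*Combined protocol and SAP*

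**What the plan says.** Objective 2.2 is "To evaluate the acute and long term toxicity associated with partial breast proton therapy". Section 9.2 carries it into the analysis: "All acute toxicities will be scored according to the NCI Common Toxicity Criteria v2.0". It sets no minimum grade for scoring, and it asks for toxicity frequencies to be tabulated and compared with the literature. It also gives a separate route for severe events: "Any toxicities with a threshold of Grade 3 or above will be reported as an adverse event". Late toxicity is scored on a different scale (RTOG), but no time point divides acute from late.

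Section 8.1 fixes the visits. Its row "Toxicity Assessment" is marked before treatment, at 1 month after treatment, and from 6 months after treatment at six-monthly intervals, becoming annual at year 5. The table has no column for the treatment period or its last day.

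Section 5.4.1 delivers treatment in "10 equal fractions over ten treatments days". The procedure that section 5.4.3 attaches to every attendance is imaging: "Orthogonal localization radiographs to be taken prior to each treatment". No toxicity grading is attached to those days.

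Section 7.1 allows chemotherapy or hormonal therapy once proton therapy is complete, and sets no minimum interval.

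**The concern.** A tabulated frequency needs a defined observation window. Section 9.2 promises every acute toxicity, but the schedule meant to supply the data starts observing after treatment has been over for a month. Two assessors could both follow the protocol and produce different acute rates from the same patients: one records what is present at the 1-month visit, the other the worst grade since the first fraction.

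Low-grade reactions are where this matters. Grade 3 or above has its own reporting route; Grade 1-2 has none. The external-beam partial-breast series described in section 1.0 reports reactions of mainly this kind, mild to moderate in degree. The protocol also expects proton therapy to be less toxic than conformal radiotherapy, so low-grade frequencies bear on the comparison that 9.2 promises. A transient reaction that nobody grades at the time cannot be reliably reconstructed later.

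A second problem lies at the same visit. Because 7.1 sets no interval, the first score after baseline may be taken when systemic therapy is already under way, and its effects could then be counted with those of proton therapy.

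**Working it through.** The plan states no acute toxicity rate, so there is no figure of its own to reproduce. The check has two parts.

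**1. When the first score after baseline falls**

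Inputs: ten fractions on ten treatment days (5.4.1) and first post-treatment score at 1 month (8.1). Assumptions: 1 month means 28 to 31 days, it runs from the last fraction, and no holidays intervene. The documents do not say whether treatment days are weekdays only, so both cases are shown.

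Days from first to first scored visit = (days from first to last fraction) + (28 to 31).

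- Weekdays only, Monday start: the last fraction is on day 11. 11 + 28 = 39; 11 + 31 = 42.
- Weekdays only, any other start day: two weekends intervene, so the last fraction is on day 13. 13 + 28 = 41; 13 + 31 = 44.
- Ten consecutive calendar days: the last fraction is on day 9. 9 + 28 = 37; 9 + 31 = 40.

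Overall range: 37 to 44 days from the first fraction, of which 28 to 31 follow the last.

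**2. Which routes could capture a reaction in that interval**

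- *8.1, toxicity row.* Nothing is marked between the pre-treatment and 1-month visits. No recall period or worst-grade instruction is attached to the 1-month score.
- *8.1, history and physical.* This is marked at the same 1-month visit. A history may bring out a reaction that has settled, but no CTC grade is required for it.
- *5.4.3, daily imaging.* Patients attend on every treatment day, so scoring would be practical, but none is requested.
- *9.4, treatment records.* These are collected and kept, and may contain notes of reactions. They carry no grading requirement.
- *9.2, adverse event reporting.* This covers Grade 3 or above and is not tied to a visit. Grade 1-2 is outside it.
- *9.2, the general commitment.* Cosmesis is graded "periodically following treatment according to section 8.1" (section 8.2) and photographs are taken "periodically following proton therapy per section 8.1" (section 8.3). The toxicity sentence in 9.2 has no such tie to 8.1. It can be read as a standing duty, with 8.1 giving the minimum visits. Even so, it supplies no form, date or interval for scoring on treatment.

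A Grade 1-2 reaction that appears and settles between the first fraction and the 1-month visit therefore has possible informal routes and no scheduled graded one.

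**Size.** No section says when reactions appear or resolve, how often they occur, or what share would be recalled. The external-beam series in section 1.0 gives no timing and was treated twice daily over 5 days, a different schedule. A numerical estimate of the loss would rest wholly on assumed inputs, so none is given.

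**The case against.** The strongest reply is that the data may be captured anyway. The 1-month visit includes a history, which normally covers events since the last contact. The department keeps treatment records, patients are seen on every treatment day, and 9.2 can be read as a duty to score whenever toxicity occurs. Severe events are reported regardless of the schedule. The analysis is descriptive tabulation with no hypothesis or threshold attached. Most of this stands, and it limits the point to low-grade, transient reactions. It does not close the gap, because none of these routes requires a CTC grade for such a reaction or defines the window over which a frequency is counted.

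A second reply is that one sentence would do: have the 1-month form record the worst grade since the first fraction. That would close the gap in the rules, but the grade would then depend on recall over 37 to 44 days. A score at the last fraction shortens that recall.

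A reader might infer more than the documents support, in three ways:

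- *That the acute rates will be too low.* Missed reactions alone push them down, but systemic therapy under 7.1 could push the 1-month score up. The net direction is not established.
- *That the comparison with published reports will favour this trial.* That would require those reports to have scored during treatment, which the documents do not say.
- *That the toxicity evaluation after the first 25 subjects (9.1) is compromised.* Section 9.1 states no grade, rate or time window for it, so the documents give no basis for that claim.

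**Conclusion.** The point holds as a mismatch between the schedule and the scoring commitment. The plan undertakes to score all acute toxicity, but its first scheduled score after baseline comes about 37 to 44 days after treatment starts, with no worst-grade or recall rule. Grade 1-2 reactions that settle before then have no scheduled graded capture. Under-recording is possible and is not shown; its size and the net direction of error cannot be computed from the documents.

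The interval rests on the assumptions listed with the calculation. Treating the 1-month visit as the acute assessment, and 6 months onward as late, is also an assumption, because 9.2 draws no boundary. Confidence is high about the omission and not about any bias. The change should be made because it is cheap and the information is lost if not collected at the time. The planned tabulation is not invalid without it.

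**What to change.** Reconcile 8.1 with 9.2:

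- **In 8.1**, add a CTC v2.0 toxicity score at the last fraction, covering the interval since the first fraction.
- **On the 1-month form**, record the worst grade since the last fraction, and whether systemic therapy had started by then.
- **In 9.2**, define the acute frequency as the worst grade from the first fraction to the 1-month visit. This also supplies the missing boundary for acute toxicity. Show the worst on-treatment grade alongside, labelled as on-treatment only, because it leaves out reactions that appear after the last fraction. State that the figure to 1 month can include effects of systemic therapy.

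The cost is one short form per patient, on a day the patient already attends, and a sentence or two in 9.2. Reported acute rates may be higher than under the present schedule. The change concerns data capture only and touches no dose, treatment schedule or clinical rule.

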5.0 Radiation Therapy

- 5.1 Radiation therapy will start within 4 weeks of surgical resection
- 5.2 Immobilization and treatment planning CT scan of the chest.
- 5.3 Treatment Planning
 - 5.3.1 Outline tumor bed using surgical clips and clinical information
 - 5.3.2 Add 1 cm in all directions to create clinical target volume (CTV) excluding chest wall and skin.
 - 5.3.3 Create multi-field treatment plan with the 90% isodose covering the CTV while the skin surface receives no more than 70%.

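### Section 9.2 gives the pre-treatment toxicity score no role, so surgical findings that persist can be counted as proton toxicity

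*Combined protocol and SAP*

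**What the plan says.** The study parameters table in section 8.1 has a row "Toxicity Assessment" marked before treatment, at 1 month after treatment, and then every 6 months from month 6, becoming annual from year 5. A baseline toxicity score is therefore planned for every patient.

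Two other sections bear on what that score will contain. Section 5.1 states that "Radiation therapy will start within 4 weeks of surgical resection". Section 8.3 states that "Photographs will be taken of the post-surgical breast and periodically following proton therapy per section 8.1", and section 8.1 marks photographs at the pre-treatment visit.

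Section 9.2 gives the scoring and the analysis in four sentences. The first sets the scale for the acute period: "All acute toxicities will be scored according to the NCI Common Toxicity Criteria v2.0". The next two name the RTOG scale for late effects and make Grade 3 the level from which an event is reported as adverse. The analysis itself is the last sentence: "Frequencies of toxicities will be tabulated and compared to published reports". None of the four mentions the pre-treatment score.

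The objective served is 2.2: "To evaluate the acute and long term toxicity associated with partial breast proton therapy". Section 9.1 also makes enrolment beyond the first 25 subjects depend on a toxicity evaluation being judged acceptable, without a numerical threshold.

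**The concern.** Objective 2.2 concerns toxicity associated with protons, whereas section 9.2 describes a count of toxicities. The two differ if patients still have findings from lumpectomy or axillary surgery when they are scored after protons. A randomized control group would show that background rate. This trial has one arm, so the separation has to come from within the patient, by comparison with the pre-treatment score, or from a stated attribution rule. The plan schedules the first without using it and does not state the second.

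Low grades are where this matters. The 3D conformal external-beam series described in the introduction reported mild fatigue, mild breast tenderness and mild to moderate skin reactions. Fatigue and tenderness can plausibly follow surgery too. The introduction expects protons to be less toxic than that technique, so a count that includes surgical findings could work against the trial's own rationale. Because 9.2 leaves the counting rule open, the choice could also be made after the data are seen.

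**Working it through.** The documents give no toxicity rate, error rate or power, so there is no stated figure to reproduce. The check is a reading of the sections together, followed by an illustration on assumed values.

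**1. Does the pre-treatment visit follow surgery?** Section 8.1 does not say so directly. It marks photographs at that visit, and 8.3 describes the photographs as being of the breast after surgery. Eligibility also needs surgical results: margins (3.6) and, for invasive disease, nodal pathology (3.4). The visit therefore appears to follow surgery.

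**2. Is the score used anywhere?** Sections 8 and 9 contain no change from baseline, no definition of treatment-emergent toxicity and no attribution rule. No section says that findings present before protons will be counted, and none says that they will be excluded.

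**3. Could a surgical finding still be present when scored?** Protons start within 4 weeks of resection (5.1) and run over ten treatment days (5.4.1), about 2 weeks if five days a week are assumed. The first follow-up is 1 month later, about 4 weeks.

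- Surgery to first follow-up: at most about 4 + 2 + 4 = 10 weeks.
- Persistence needed from a pre-treatment score taken just before protons: about 2 + 4 = 6 weeks for the 1-month visit, and more than 6 months for the next one.

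Persistence is plausible at 1 month and less so later. The documents give no rate for either.

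**4. Illustration of size.** For one toxicity item, let *b* be the share of patients with a pre-treatment finding that persists after protons, and *p* the true rate of new or worsened toxicity, with the two independent. Both are assumed.

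- Tabulated rate with no baseline rule = 1 − (1 − *b*)(1 − *p*)
- Excess over the true rate = *b*(1 − *p*)

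With *p* = 10%:

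| *b* | Tabulated rate | Excess (points) | Expected of 25 (true 2.5) | Expected of 50 (true 5.0) |
|---|---|---|---|---|
| 0% | 10.0% | 0 | 2.50 | 5.00 |
| 5% | 1 − 0.95 × 0.90 = 14.5% | 4.5 | 3.63 | 7.25 |
| 10% | 1 − 0.90 × 0.90 = 19.0% | 9.0 | 4.75 | 9.50 |
| 20% | 1 − 0.80 × 0.90 = 28.0% | 18.0 | 7.00 | 14.00 |
| 30% | 1 − 0.70 × 0.90 = 37.0% | 27.0 | 9.25 | 18.50 |

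The excess shrinks as *p* rises. At *b* = 30% it is 0.30 × 0.98 = 29.4 points for *p* = 2%, and 0.30 × 0.70 = 21 points for *p* = 30%. At Grade 3 or above *b* is likely close to zero, and so is the excess.

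**5. Can a change in grade be computed?** Acute toxicity uses CTC v2.0 and late toxicity uses the RTOG scale. The plan does not say which scale applies at the pre-treatment visit. A change in grade is well defined only where the pre-treatment and later scores share a scale.

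**The case against.** A reader might infer that 9.2 lays down an unadjusted count, so that surgical effects will be reported as proton toxicity and the frequencies are overstated. The text does not go that far. It says that frequencies will be tabulated, not that they will be unadjusted. The wording of objective 2.2 and the existence of a baseline score both fit a treatment-related tabulation. What remains is a gap that permits the miscount.

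A reader might also infer harm to the comparison with published reports and to the 25-subject evaluation. Neither is shown. The partial-breast series in the introduction treated patients after lumpectomy and may carry the same surgical background. If they reported worst grade without adjustment, an unadjusted count is the like-for-like one and an adjusted count would favour protons. The documents do not say how those series counted. The 9.1 evaluation has no numerical limit for a low-grade count to cross, and investigators can weigh baseline findings when they make it. The only grade threshold in 9.2 is Grade 3, where the effect is likely small. The documents also do not say whether that evaluation has already taken place.

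Three further limits stand. The baseline score is not the only means of separation, since clinical attribution and time course also help, although the plan specifies neither. A rule that counts only rises in grade would hide a surgical finding that fails to resolve. And such a rule does not remove effects of the chemotherapy or hormonal therapy that section 7.1 allows after protons.

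These points narrow the claim and shape the remedy. They do not explain why a scheduled baseline assessment has no place in the analysis.

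**Conclusion.** The point holds as a risk that 9.2 leaves open. A toxicity score is planned before protons, apparently after surgery, and the analysis section gives it no role. Low-grade surgical findings that persist to a follow-up visit can therefore be counted, and the frequencies may overstate toxicity associated with protons.

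The documents do not fix the size. It depends on how many pre-treatment findings persist, and at what grade. The illustrated excess of 4.5 to 27 points at *p* = 10% rests wholly on assumed persistence of 5% to 30% and on independence. It falls to zero if nothing persists, or if baseline findings are set aside in practice. Bias in the historical comparison or in the 9.1 decision is possible but not established. No sample size or error rate is affected.

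**What to change.** Add to section 9.2:

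- **Acute toxicity (CTC v2.0).** For each item, tabulate side by side the pre-treatment grade, the worst post-treatment grade, and the number of patients whose grade is new or worsened relative to pre-treatment. Use the new-or-worsened count to describe toxicity associated with protons.
- **Worst grade.** Keep it in the table, for comparison with published reports that give only that, and so that findings that fail to resolve stay visible.
- **Late toxicity (RTOG).** Show the pre-treatment finding beside the late grade. Apply the new-or-worsened count only to items scored on the same scale at both times.
- **Section 9.1 evaluation.** Present all three acute columns there.

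The cost is a few extra table columns. The pre-treatment assessment is already scheduled, so no visit or subject is added. Effects of later systemic therapy remain in the new-or-worsened count, and the table should say so.
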